3.1. General principles

Unless stated otherwise, analyses will be performed using SPSS statistics V27 (IBM, Armonk, New York) or higher.

Prior to performing a hard database lock, all variables will be checked including any outliers. Any missing or outlying values with be checked with the investigator at the corresponding site.

3.2. Interim analyses

The DSMB will perform two interim analyses, when data are available, of 33% and 66% of the patients for safety concerning the occurrence of death, HF hospitalisations and acute kidney injury.

The objective of the interim analysis will be to assess the following:

- Safety: is there any difference in the safety profile between treatment groups?
- Are there any other observations in the accumulated data that should be communicated to the sponsor?

The following will be the main parameters of interest for the DSMB:

- The occurrence of HF hospitalisations
- The occurrence of death
- The occurrence of acute kidney injury

All appropriate safety measures will be summarized for the safety population by treatment for the treatment period. Safety measures will be reported per treatment group, the number (n) and percentage (%) of patients experiencing at least one event. The denominator for computation of percentages is the safety population within each treatment group.

There are no interim analyses for efficacy.

3.3. Multiplicity adjustment

The primary and key secondary endpoints will be tested hierarchically. Other secondary endpoints will be considered supportive only and there will no corrections for multiple testing.

3.4. Blind review

An independent EAC will adjudicate the cause of death and any hospitalisations as either HF-related or not, and will be blinded to treatment allocation. The events of interest will be adjudicated according to a predefined scheme based on the consensus of two committee members; in case of no consensus, the third committee member will provide final adjudication.

The members of the steering committee and the principal investigator of the sponsor site, Radboudumc, are blinded to the randomisation group. After database lock, the analysis will be performed with knowledge of randomisation.

3.5. Data sets to be analysed

The intention-to-treat principle will be used for the primary analysis.

In addition, an analysis according to the per-protocol principle will be performed. The patient-reported fluid intake in week 6 will be used to assess whether the patients in the fluid restriction arm

did adhere to the fluid restriction of 1500 ml/day, as described in '3.8 Compliance to study intervention'. Patients who were non-compliant according to '3.8 Compliance to study intervention', will be excluded from the per-protocol analysis. Non-adherence is considered not possible for the liberal fluid intake arm, therefore all liberal fluid intake patients will be included in the per-protocol analysis.

3.6. Subject disposition

The study disposition figure will include:

- Number of patients screened
- Number of screen failures and retracted IC before randomisation
- Number of patients enrolled
- Number of patients randomised per intervention group
- Number of patients lost to follow-up

3.7. Patient characteristics and baseline comparisons

Baseline descriptive statistics will be presented both in text (for certain characteristics) and in table. Categorical variables will be presented with numbers (percentages) and compared using a Chi-squared test or Fisher exact test, whichever is appropriate. Continuous variables will be assessed for normal distribution and reported as means (standard deviation) or medians (interquartile range), whichever is appropriate. Baseline characteristics will be presented by randomisation group and for the overall population.

The following characteristics will be presented:

- Age
- Sex at birth
- Race
- Baseline KCCQ-OSS
- Baseline TDS-HF
- NYHA Class
- Ejection fraction (percentage, HFrEF, HFpEF)
- Pathogenesis of heart failure (ischemic, dilating, hypertension, valvular, drug-induced, other, unknown)
- Heart failure duration
- Medical history (current fluid management, atrial fibrillation/flutter, BMI, COPD, DM, hypertension, currently smoking)
- Laboratory values (haemoglobin, sodium, potassium, urea, eGFR, NT-proBNP, osmolality)
- Concomitant therapies (see below)

3.8. Compliance to study intervention

The patient-reported fluid intake in week 6 will be used to assess whether the patients in the fluid restriction arm did adhere to the fluid restriction. Patients are considered as compliant in case daily fluid intake did not exceed 1500 ml in at least 5 of 7 days according to the patient-reported fluid intake in week 6. Besides that, adherence is questioned during the month 3 visit. However, the latter will only be reported descriptively and will not formally be used for the assessment of therapy adherence. Non-adherence is considered not possible for the liberal fluid intake arm.

3.9. Concomitant therapies

Concomitant medication will be focused on HF therapy and will be presented as numbers and percentages and in accordance with '3.7 Patient characteristics and baseline comparisons'.

The following concomitant therapies will be presented at least:

- ACEi
- ARB
- ARNI
- BB
- Digoxin
- MRA
- Loop diuretics
- Thiazides
- SGLT2i
- ICD
- CRT
- GDMT score

The GDMT score was primarily developed by the Scientific Expert Panel From the Heart Failure Collaboratory and Academic Research Consortium, and later updated with the latest HF guidelines, to improve comparability between HF trials for HFrEF patients (12, 13).

GDMT score is calculated by adding scores of each drug class. RAAS Inhibition is assigned 0 (no treatment), 1 (ACEi/ARB, <50% max daily dose), 2 (ACEi/ARB, ≥50% max daily dose) or 3 (ARNI, any dose) points. For BB, 0 (no treatment), 1 (<50% max daily dose) or 2 (≥50% max daily dose) points are assigned. MRA and SGLT2i are assigned 0 (no treatment) or 2 (any dose) points. Ivabradine, vericiguat and hydralazine and isosorbide dinitrate are assigned 0 (no treatment) or 1 (any dose) points.

The total GDMT scores will be assessed for normal distribution and reported as means (standard deviation) or medians (interquartile range), whichever is appropriate.

3.10. Analysis of the primary outcome

3.10.1. Main analysis

The difference between the two treatment arms in QoL after 3 months, as assessed with KCCQ-OSS, will be tested with the use of an ANCOVA analysis, using baseline QoL as a covariate. The difference will be presented as the average treatment effect for liberal fluid – restricted fluid arm. The estimated difference will be presented with a point estimate and 95% confidence interval. A p-value of <0.05 will be considered significant.

For the primary analysis, the intention-to-treat principle will be applied.

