2.5. Randomisation and blinding

Randomisation takes place after the patient is eligible according to the inclusion and exclusion criteria and has provided informed consent and completed the QoL questionnaires. Patients are randomised 1:1 to either liberal fluid intake or standard fluid restriction using Castor EDC with a random block randomisation algorithm and stratified randomisation per each including centre. A patient cannot be randomised more than once in the study.

Members of the steering committee and Event Adjudication Committee (EAC) members are blinded to randomisation.

The coordinating investigator (JH) and DSMB members are not blinded. The coordinating investigator (JH) prepares the data overview for the statistician of the DSMB who performs the interim analysis. The data overview is not shared with the members of the steering committee or EAC members.

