3.10.2. Adjusted analyses

Not applicable.

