3.10.3. Subgroup analyses

The following prespecified subgroups will be analysed in relation to the primary endpoint: Sex at birth (male/female), including centre, HF type based on last known EF (HFrEF ≤40%/HFmrEF 41-49%/HFpEF ≥50%), NYHA class (II/III), age (above/below median), BMI (above/below median), baseline diuretic dosage (above/below median), DM (yes/no), and baseline sodium, urea, creatinine, and NT-proBNP concentrations (above/below median).

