3.10.4. Treatment of missing data

In the unlikely case that any baseline scores on the KCCQ-OSS are missing, they will first be multiply imputed using imputations drawn from the distribution of the full study population.

Following this, a multiple imputation model will be specified separately by treatment arm and will include baseline and 3-month KCCQ-OSS as well as any auxiliary variables that are considered to be associated with the outcome or with the probability of missing the 3-month KCCQ scores. For the imputation procedure, m = 50 imputed datasets and the missing 3-month KCCQ scores will be imputed using predictive mean matching, type 1 and with k = 5 nearest neighbours specified (14). In the case of any missing data on the selected auxiliary variables, a fully conditional specification imputation approach will be specified with the imputation model for each variable defined according to the variable type.

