3.11. Analysis of the secondary outcomes

For the secondary parameters thirst distress, as assessed with the TDS-HF, and QoL at 3 months after randomisation, as assessed with the KCCQ-CSS, each of the KCCQ domains and the EQ-5D-5L, a similar approach as for the primary study parameters will be adopted.

The difference between groups in proportion of patients with clinically meaningful changes (defined as a difference of 5 points compared to baseline) in KCCQ-OSS and KCCQ-CSS (8, 10) and the percentage of events (death, all-cause hospitalisations, the need for iv-loop diuretics and acute kidney injury) will be tested with Chi-square or Fisher exact test, whichever appropriate. The

difference in between groups patient reported fluid intake will be analysed with a Students' t test or Mann-Whitney U test, whichever appropriate.

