3.12. Analysis of other outcomes

Time-to-event outcomes will be analysed using a Cox proportional hazards model, with, if necessary, baseline covariate adjustment in case of unexpected differences in baseline descriptive statistics. The estimated treatment effect will be presented in the form of hazard ratios with 95% confidence intervals. Kaplan-Meier plots will be used to present the pattern of events per treatment group over the follow-up period. The assumption of proportional hazards will be checked using statistical tests and graphical diagnostics based on the Schoenfeld residuals.

The exploratory safety endpoint will be assessed using a unmatched win ratio approach (16). Patients from the liberal fluid intake arm will be paired with every single patient from the standard fluid restriction arm. For each pair the better clinical outcome will be determined in the following sequential criteria and will stop after either patient has shown profit.

A 'win' is defined as the patient in the liberal fluid intake arm has the better outcome compared to the patient in the standard fluid restriction group. A 'loss' is defined in the opposite manner.

- 1. Death within 6 months follow-up
 - a. Death is worse than no death
 - b. Tied, if not possible to determine
- 2. HF hospitalisations within 6 months follow-up
 - a. More HF hospitalisations is worse
 - b. Tied, if not possible to determine
- 3. Requirement of iv-loop diuretics within 6 months follow-up
 - a. More events is worse
 - b. Tied, if not possible to determine
- 4. All-cause hospitalisation within 6 months follow-up
 - a. More all-cause hospitalisations is worse
 - b. Tied, if not possible to determine

The win ratio is: total number of wins / total number of losses.

The win difference is: percentage of wins minus percentage of loses.

4. Prespecified subanalyses

All patient characteristics of the prespecified subanalyses listed below will be presented in accordance with '3.7 Patient characteristics and baseline comparisons' of this document, unless stated otherwise.

Change of fluid management analysis

Aim:

- 1. To investigate the effect of liberal fluid intake versus fluid restriction in the subgroup of patients who were prescribed a fluid restriction prior to randomisation on the primary, (key) secondary and explorative endpoints

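### Randomisation is stratified by centre but the primary ANCOVA omits centre, so its interval may be slightly too wide; the exploratory Cox adjustment depends on observed baseline differences

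*SAP*

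**What the plan says.** **Randomisation.** SAP 2.5 allocates patients 1:1 "using Castor EDC with a random block randomisation algorithm and stratified randomisation per each including centre".

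**Primary model.** In SAP 3.10.1, the difference in KCCQ-OSS at 3 months "will be tested with the use of an ANCOVA analysis, using baseline QoL as a covariate". No other covariate is named, and SAP 3.10.2, on adjusted analyses, reads "Not applicable". The sample size in SAP 2.6 uses the same baseline-only ANCOVA, so 3.10.1 is not shorthand for a fuller model.

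**Other questionnaires.** For TDS-HF, KCCQ-CSS, the KCCQ domains and EQ-5D-5L, SAP 3.11 says "a similar approach as for the primary study parameters will be adopted".

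**Where centre does appear.** It is in the subgroup list of SAP 3.10.3: "Sex at birth (male/female), including centre, HF type based on last known EF". It could also be picked for the imputation model of SAP 3.10.4, which admits "any auxiliary variables that are considered to be associated with the outcome". Neither puts it in the ANCOVA.

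**Time-to-event outcomes.** These are exploratory (SAP 2.3.3). SAP 3.12 uses a Cox model "with, if necessary, baseline covariate adjustment in case of unexpected differences in baseline descriptive statistics". SAP 3.4 adds: "After database lock, the analysis will be performed with knowledge of randomisation".

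**The concern.** Blocking within centre keeps the arms nearly equal in size in every centre, so differences between centres largely cancel from the treatment contrast. A model without centre leaves those differences in its residual variance. If they exist after baseline adjustment, the standard error describes a less precise design than the one used: the interval is too wide and the true type I error falls below 5%. Because SAP 3.3 tests the primary and key secondary endpoints hierarchically, a narrow miss on KCCQ-OSS would also stop formal testing of TDS-HF.

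The Cox clause is a different problem. Under randomisation, baseline differences arise by chance, so observing one is not a sound reason to change the model. The SAP names no covariates, no threshold and no decision-maker. With allocation known at the time of analysis, adjusted and unadjusted hazard ratios could both be seen before one is chosen.

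**Working it through.** **Inputs from SAP 2.6:** difference 2.5 points, SD 20, baseline to follow-up correlation 0.88, alpha 0.05 (taken as two-sided, from the 95% interval in 3.10.1), power 80%, 454 evaluable patients, 10% drop-out.

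**1. Reproduce the plan's figure.**
- Residual variance = 400 × (1 − 0.88²) = 400 × 0.2256 = 90.24; residual SD = 9.50.
- n per arm = 2 × (1.96 + 0.8416)² × 90.24 / 2.5² = 226.7, rounded up to 227, so 454 in total. This matches.
- 454 / 0.9 = 504.4, rounded up to 505 and then to an even 506. This matches.

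**2. Precision of the planned model.**
- SE = 9.50 × √(4/454) = 0.892.
- 95% half-width = 1.96 × 0.892 = 1.75 points.
- 2.5 / SE = 2.804.

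**3. Effect of leaving centre out.** Let s be the share of the baseline-adjusted residual variance that lies between centres, and f = √(1 − s). The documents do not give s, so a range is assumed. With allocation balanced within centre:
- implied between-centre SD = √(s × 90.24)
- excess CI width = 1/f − 1
- true type I error without centre = 2 × [1 − Φ(1.96/f)]
- power without centre = 1 − Φ((1.96 − 2.804)/f)
- power with centre = 1 − Φ(1.96 − 2.804/f)

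| Assumed s | Between-centre SD (points) | Half-width with centre | CI too wide by | Type I error without centre | Power without centre | Power with centre |
|---|---|---|---|---|---|---|
| 0% | 0 | 1.75 | 0% | 5.0% | 80.1% | 80.1% |
| 2% | 1.3 | 1.73 | 1.0% | 4.8% | 80.3% | 80.8% |
| 5% | 2.1 | 1.70 | 2.6% | 4.4% | 80.7% | 82.0% |
| 10% | 3.0 | 1.66 | 5.4% | 3.9% | 81.3% | 84.0% |

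The half-width is also the smallest observed difference that reaches significance. At s = 5%, a result between 1.70 and 1.75 points would be significant only with centre in the model.

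**4. Simulation check.** There were 20,000 trials per setting, with four centres, random blocks of 4 or 6 within centre, and two patterns of centre size (near-equal, and 200/130/80/44). Block and centre sizes are assumptions. At s = 10%, type I error was 3.8% without centre and 4.9% with it; power was 80.9–81.2% without and 83.7–83.9% with. At s = 0 the two models agreed. Monte Carlo SE is about 0.15 points for type I error and 0.28 for power.

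**5. Key secondary outcome.** For TDS-HF (1.5 points, SD 8, correlation 0.88, SAP 2.6), SE = 8 × √0.2256 × √(4/454) = 0.357 and 1.5 / SE = 4.206. Power is already 98.8%. At s = 10% it is 99.1% without centre and 99.3% with, a gain below 0.3 points.

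**6. The Cox trigger.** SAP 3.7 and 3.9 list about 22 categorical baseline items, to be compared by chi-squared or Fisher tests. If the trigger were p < 0.05 and the tests independent (both assumptions; the SAP states neither), the chance of at least one such difference is 1 − 0.95²² = 68%. This shows only how easily an undefined trigger could be met.

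**The case against.** The strongest reply is that nothing goes wrong without centre: the estimate is unbiased, the error is conservative, the sample size stands and power stays at its planned level. The gain rests on an assumed variance share. The 10% case implies a between-centre SD of about 3.0 points after baseline adjustment, more than the 2.5-point effect the trial is built to detect. Baseline score already removes 77% of the variance (0.88² = 0.774), including much of any case-mix difference between centres. At a 2% share the gain is about half a power point. All of this stands. It limits the size of the point, but it gives no reason to leave out the stratification factor when including it costs almost nothing.

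On the Cox models, the unadjusted analysis appears to be the default and the outcomes are exploratory. The event percentages in SAP 3.11 use chi-square or Fisher tests and are untouched. That also stands, but the clause still leaves covariates and trigger undefined.

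Finally, the protocol file available is a response letter to a journal's statistical review, not protocol version 4.2 itself. Wording on centre elsewhere cannot be excluded, but the SAP should state the model in full.

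**Conclusion.** The concern holds. The primary and related ANCOVAs omit the factor by which patients are randomised. For an assumed centre share of 0 to 10% of residual variance, the primary confidence interval is 0 to 5.4% too wide and the possible power forgone is 0 to about 3 points. The upper end needs large centre differences, and the effect is nil if centre is not prognostic once baseline is in the model. There is no bias, no inflation of type I error and no shortfall against the planned 80% power. The effect on TDS-HF is negligible.

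The imbalance-triggered Cox adjustment is a separate gap in prespecification, confined to exploratory outcomes. No size can be put on its effect on the hazard ratios. Both parts should be corrected; neither threatens the trial's validity.

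**What to change.** - **SAP 3.10.1 and 3.11:** fit the ANCOVA with treatment, baseline score and centre as a fixed effect. State a minimum centre size below which centres are pooled, and how, before database lock. Amend 3.10.2 if needed so that it does not contradict this.
- **SAP 3.10.4:** name centre in the imputation model. Imputation is done separately by arm with five nearest neighbours, which divides small centres further, so apply the same pooling rule there.
- **SAP 3.12:** delete the conditional clause. Write down one model before database lock and use it whatever the baseline table shows: either treatment alone, or treatment with a named covariate set. If centre is to be a stratum or covariate, state in advance the event count needed and the fallback.

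**Cost:** SAP wording only. Centre is already recorded, and no sample size, visit or data item changes. With four centres the primary model loses 3 of about 450 degrees of freedom. Four is the number participating at the time of the response letter (Appendix A, Minor Concerns); the final number is not stated.

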3.10.2. Adjusted analyses

Not applicable.

3.10.3. Subgroup analyses

The following prespecified subgroups will be analysed in relation to the primary endpoint: Sex at birth (male/female), including centre, HF type based on last known EF (HFrEF ≤40%/HFmrEF 41-49%/HFpEF ≥50%), NYHA class (II/III), age (above/below median), BMI (above/below median), baseline diuretic dosage (above/below median), DM (yes/no), and baseline sodium, urea, creatinine, and NT-proBNP concentrations (above/below median).

3.10.4. Treatment of missing data

In the unlikely case that any baseline scores on the KCCQ-OSS are missing, they will first be multiply imputed using imputations drawn from the distribution of the full study population.

Following this, a multiple imputation model will be specified separately by treatment arm and will include baseline and 3-month KCCQ-OSS as well as any auxiliary variables that are considered to be associated with the outcome or with the probability of missing the 3-month KCCQ scores. For the imputation procedure, m = 50 imputed datasets and the missing 3-month KCCQ scores will be imputed using predictive mean matching, type 1 and with k = 5 nearest neighbours specified (14). In the case of any missing data on the selected auxiliary variables, a fully conditional specification imputation approach will be specified with the imputation model for each variable defined according to the variable type.

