We do not expect any missing baseline QoL measurements because they must be completed before randomisation and are filled out in a digital manner in which completion is mandatory and entry errors are impossible. Besides, due to the method of scoring, the KCCQ will always provide an Overall Summary Score, based on a mean of the available other summary scores. For the unlikely case where a baseline value is missing, we have taken on the advice of the reviewer and proposed that multiple imputation is also used for these values (page 7, line 22-27).

Regarding the missing QoL measurements at follow up, it is agreed that the assumption that these data are missing at random is a strong assumption, and agree that sensitivity analyses for which these data are assumed to be missing not at random should be performed. We have now specified these in the protocol (page 8, line 3-6).

It is agreed that missing data due to death is not a missing data problem, however particularly for the KCCQ, which is predictive of clinical outcomes including death, excluding patients from the analysis who died is likely to bias the results. Therefore for our primary and sensitivity analyses we would like to retain the patients who died in the analysis. We will ensure that this issue is part of our discussion and keep an eye out for any emerging methodological research that may help to resolve this issue while allowing us to address the research question of interest.

4. The sample size calculation accounts for a 10% drop-out rate, increasing N from 454 subjects to 498 subjects. Can the authors clarify how 498 subjects were obtained? Applying the standard LTF adjustment, one gets around 506 patients (after rounding up).

We thank the reviewer for his/her suggestion and applied the LTF adjustment as suggested. We performed the calculation:  $N = n / (1-(z/100)) \rightarrow N = 454 / (1-(10/100)) = 504.4$ . Therefore, we adjusted the sample size to 506 subjects to maintain an equal distribution of subjects across both study arms (manuscript: page 9, line 12 / DSMB Charter: page 1, page 6, page 10 / Figure 1 and the Visual Take Home Graphic).

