5. In the Data Safety Monitoring Board section, the authors write "The DSMB has two mandates. First, to perform two interim analyses when data is available of 33% and 66% of the patients for safety on the occurrence of the clinical endpoints....." This is not completely accurate since the DSMB charter lists "Early stopping due to harm of a treatment or clear

superiority" as one of the possible recommendations after an IA. Therefore, the IA consists of both efficacy and safety assessments especially since KCCQ scores (the primary endpoint) is listed as one the main parameters of interest for the DSMB. Since interim looks for efficacy on the primary endpoint will increase the type I error rate of a clinical trial, please clarify how the type I error rate will be controlled. Furthermore, it may no longer be the case that the significance level for the final analysis of the primary endpoint(s) will be at 0.05 (re: "Both primary hypotheses on QoL by the KCCQ-OSS and TDS-HF will be tested at a 2-sided 5% significance level.)

We agree with the reviewer that there is a discrepancy between the original manuscript and the DSMB charter. To be clear, the objective of the DSMB is to solely assess safety. Accordingly, we have adjusted the DSMB charter. There will be no interim analyses on efficacy. We have removed the KCCQ scores as parameters of interest from the DSMB charter to avoid any misunderstanding in this regard. In addition, we have adjusted the possible recommendation "Early stopping due to harm of a treatment or clear superiority" in the DSMB charter as well. The DSMB will assess safety based on clinical event rates. We thank you for addressing this inconsistency in our documents and feel that the revised version of the DSMB charter provides more clarity.

Since no interim analyses on efficacy will be performed, there is no increase in type I error rate and no additional measures are required to control type I error rate.

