2.6. Sample size

Sample size calculation was performed with the software package G*Power 3.1.7 and performed as previously described methods for repeated measures ANCOVA analysis, using baseline QoL as a covariate (1).

For our sample size calculation, a correlation of 0.88 between baseline and follow-up KCCQ-OSS was assumed (2). Furthermore, a follow-up KCCQ-OSS of 66.25 with a standard deviation of 20 was assumed for liberal fluid intake group (3-7). Next, we assume a 2.5-point difference in KCCQ-OSS follow-up scores at 3 months between both randomisation groups (3-7). To test this difference at a p-value of 0.05 and power of 80%, we need a total of 454 evaluable patients. Anticipating a drop-out rate of 10% we aim to enrol 506 patients.

To interpret the clinical relevance of a mean difference of 2.5 points in KCCQ score, it is important to differentiate between differences in scores on a patient level or group level. Based on previous validation studies on a patient level, a change of 5, 10 and 20 points in KCCQ-OSS follow-up scores are considered small, moderate-to-large and large-to-very large clinical important changes respectively (8, 9). Moreover, even smaller changes are possibly associated with clinically important improvements or deteriorations (10). However, a mean difference on randomisation group level is not directly comparable with the clinically important changes on a patient level. Randomisation group means reflect many different outcomes amongst patients, as in each randomisation group patient's clinical status will improve, deteriorate or remain stable.

In view of the above, it is illustrative to look at the results of previous landmark trials which demonstrated positive effects on clinical outcome for the studied interventions, which are now part of guideline-directed medical therapy.

For example, in the PARADIGM-HF (sacubitril/valsartan versus enalapril), the KCCQ-OSS mean difference was 1.27 points, while the proportion of clinically important improvements was greater and the proportion of deterioration was lower for sacubitril/valsartan group compared to the enalapril group (35% versus 33% and 27% versus 31%, respectively) (7).

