3.10.5. Other sensitivity analyses

The main analysis for the primary outcome will be performed also according to the per-protocol principle. The per-protocol population is defined as described in '3.5. Data sets to be analysed'.

A sensitivity analysis will be performed to examine the sensitivity of the results to missing data assumptions. For this sensitivity analysis, a delta-adjustment approach will be applied, with a fixed constant (to be elicited from a panel of experts) added to the values imputed under the standard missing at random procedure (15).

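### No planned KCCQ analysis separates deaths before month 3 from other missing scores, so the quality-of-life result is not tested against a mortality imbalance

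*SAP*

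**What the plan says.** - **Imputation (SAP 3.10.4).** Missing 3-month KCCQ-OSS values are "imputed using predictive mean matching, type 1 and with k = 5 nearest neighbours specified". The model is fitted separately by arm, with baseline KCCQ-OSS and auxiliary variables, and 50 datasets are created. The section does not mention death.
- **Deaths (Protocol document, Appendix A, Major Concerns, reply to comment 3).** The sponsor agrees that death does not create missing data in the usual sense. It argues that leaving deaths out would probably bias the results, and concludes: "for our primary and sensitivity analyses we would like to retain the patients who died in the analysis". The issue is left to the discussion and to any new methods that may appear.
- **Sensitivity analyses (SAP 3.10.5).** One is per-protocol. Under 3.5 it excludes only non-compliant patients in the restriction arm. The other is a delta adjustment: a constant, still to be elicited from experts, is "added to the values imputed under the standard missing at random procedure". The reason for missingness plays no part.
- **Where death does count.** It is in the safety composite (2.3.2), the exploratory safety outcomes (2.3.3), the interim safety looks (3.2), the event percentages (3.11), and the Cox models and win ratio (3.12). The draft outcomes table in Appendix 1 has a row for death by arm. None of these analyses includes KCCQ.

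**The concern.** Predictive mean matching gives each missing case a score that was actually observed in another patient. An observed 3-month score requires a living respondent, so a patient who died before month 3 receives a survivor's score. In the primary analysis, expected KCCQ differences therefore hardly respond to an imbalance in early deaths.

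The delta analysis does not fill this gap. It moves imputed scores, but by the same planned constant for a death as for a living patient who did not return the questionnaire. A constant that is plausible for the second group need not be plausible for the first.

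The trial tests relaxing a restriction that the SAP calls standard practice, and safety is one of its own questions. If deaths by month 3 were unequal, readers would ask whether the quality-of-life conclusion still holds once death counts as a bad outcome. No planned KCCQ analysis answers that. SAP 3.11 carries a similar approach over to KCCQ-CSS, the KCCQ domains and EQ-5D-5L, so the gap extends to them.

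**Working it through.** **Inputs (SAP 2.6 unless stated)**
- Target: "we assume a 2.5-point difference in KCCQ-OSS follow-up scores at 3 months between both randomisation groups".
- Mean and SD: "a follow-up KCCQ-OSS of 66.25 with a standard deviation of 20 was assumed for liberal fluid intake group". If the difference favours liberal intake, the restricted-arm mean is 66.25 − 2.5 = 63.75.
- Correlation: "a correlation of 0.88 between baseline and follow-up KCCQ-OSS was assumed".
- Size: "To test this difference at a p-value of 0.05 and power of 80%, we need a total of 454 evaluable patients". The enrolment target is 506, or 253 per arm.
- Sidedness: the SAP does not state it. The only mention is manuscript text cited in the journal's comment 5: "will be tested at a 2-sided 5% significance level".
- Assumptions, not in the documents: the number of deaths by month 3, a score of 0 for death, and a donor score of 45 for a death matched to a sicker survivor.

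**Step 1: reproduce the plan's figure**
- ANCOVA residual SD = 20 × √(1 − 0.88²) = 9.50.
- n per arm = 2 × (1.96 + 0.842)² × 9.50² / 2.5², which rounds up to 227, so 454 in total.
- 454 / 0.9 = 504.4, rounded up to 505 and made even at 506.

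Both figures agree with the SAP, and two-sided 5% is the reading that gives 454.

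**Step 2: shift per excess death**

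Scoring a death 0 instead of donor score s moves an arm mean by s / 253.
- s = 66.25 (average donor): 66.25 / 253 = 0.26 points.
- s = 45 (sicker donor): 45 / 253 = 0.18 points.

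**Step 3: illustrative imbalances, average donor, difference as liberal minus restricted**

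| Deaths, liberal v restricted | Calculation | Difference |
|---|---|---|
| 0 v 0 | 66.25 − 63.75 | 2.50 |
| 3 v 0 | 66.25 × 250/253 − 63.75 | 1.71 |
| 0 v 3 | 66.25 − 63.75 × 250/253 | 3.26 |
| 3 v 3 | (66.25 − 63.75) × 250/253 | 2.47 |

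For 3 v 0 the shift is 3 × 66.25 / 253 = 0.79 points (31% of 2.5) with an average donor, and 3 × 45 / 253 = 0.53 points (21%) with the sicker donor. The standard error is 9.50 × √(2/253) = 0.84 with 253 per arm and 9.50 × √(2/227) = 0.89 with 227. The 0.79-point shift is thus about 0.9 standard errors on either basis. Offsetting the whole 2.5 points would take about 2.5 / 0.26 ≈ 10 excess deaths.

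**Step 4: what the planned delta analysis can show**

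With an assumed delta of −10, one excess imputed patient moves the difference by 10 / 253 = 0.04 points. That compares with 0.18 to 0.26 in step 2.

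**Step 5: cost of scoring 0 in the mean-based ANCOVA**

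Let a proportion p die in each arm, independently of baseline, with a mean of 65 midway between the arms. Residual variance = (1 − p) × 20² + p(1 − p) × 65² − [(1 − p) × 0.88 × 20]². The effect becomes 2.5(1 − p).

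| p | Residual SD | Power, 253 per arm |
|---|---|---|
| 0 | 9.50 | 84% |
| 0.5% | 10.6 | 75% |
| 1% | 11.6 | 67% |
| 2% | 13.3 | 54% |
| 3% | 14.8 | 45% |

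**The case against.** **Death is assessed elsewhere, by design.** Quality of life is the primary objective and mortality is a safety matter. Death enters the composite, the event tests, the Cox models, the top tier of the win ratio and the interim safety looks, and the draft table shows deaths by arm. This stands. A reader might infer that no planned analysis treats death as an adverse outcome, and the SAP plainly contradicts that. The gap is confined to the KCCQ and related quality-of-life analyses.

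**Keeping deaths in was reasoned and disclosed.** A reader might also infer that the primary estimate is simply biased towards the arm with more deaths. That holds only against an estimand that gives death a bad score, which the trial did not adopt. The stated treatment-policy approach (Appendix A, reply to comment 6) concerns departures from fluid advice and does not say what score a deceased patient has. The choice is open to debate, but it is not an error in itself.

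**Imputed scores may be low.** Baseline KCCQ-OSS and auxiliary variables can match deaths to sicker survivors, and the delta moves them further. This stands too, and makes 0.26 points per death an upper-end figure.

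**Deaths will probably be few.** NYHA class IV, recent HF admission and life expectancy under 6 months are exclusions (2.2.2). The documents give no expected number, and nothing in them supports a 3 v 0 split in particular.

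**The evidence is indirect.** Section 3.10.4 is silent on death. That deaths are imputed follows from the lack of an exception, read with the reply letter.

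None of these points supplies a KCCQ analysis that separates death from other missingness.

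**Conclusion.** The point holds for the KCCQ analyses. Deaths before month 3 receive scores donated by survivors in the same arm, and the only missing-data sensitivity analysis makes no distinction for them. The plan therefore cannot show whether the quality-of-life result is robust to a mortality imbalance.

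The size depends on the imbalance. It is at most about 0.26 points per excess death, or about 0.18 with a donor near 45, and 0.5 to 0.8 points for an assumed 3 v 0 split against the 2.5-point target. With few, balanced deaths it is negligible: 2.47 instead of 2.50 at 3 v 3. These figures rest on 253 per arm, the SAP's means, an assumed number of deaths, and the convention that death scores 0. The sample size is unaffected. This is a cheap improvement to the robustness checks, not a reason to change the primary analysis.

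**What to change.** Leave the primary analysis as it is and change SAP 3.10.5 in two places:

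1. **Add one prespecified supplementary analysis that handles deaths before month 3 separately.** Preferably use worst rank: within each imputed dataset, rank deaths below every KCCQ-OSS value of patients not known to have died, keep the planned imputation for those patients, and fit a rank-based ANCOVA with baseline as covariate. State how ties among deaths are treated. A worst score of 0 in the planned ANCOVA is an alternative that gives a result in KCCQ points.
2. **Apply the delta shift only to missing scores of patients not known to have died.**

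The cost is SAP wording and one extra analysis run. No new data are needed, because the time-to-event analyses already require dates of death. The downside is noise: at an assumed 1% of deaths per arm, a score of 0 raises the residual SD from 9.50 to 11.6 and cuts power from 84% to 67%. The new analysis should therefore stay supportive and not replace the primary. Reporting of deaths by arm needs no change, since the draft outcomes table already foresees it.
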